**Aim 2: Determine if FUM characteristics correlate with OAB symptoms.**

At baseline and 12 weeks, we will use the overactive bladder questionnaire (OAB-q) [14] to evaluate symptoms and determine if PFM characteristics (e.g., composition, diversity, abundance, specific organisms) and AMP levels (gene expression and protein levels) correlate with patient symptoms. Relevant questions include: Does response to estrogen associate with pre-treatment PFM and/or AMP characteristics? Do PFM and/or AMP changes correlate with treatment response?

**Significance:** The medical field is beginning to adopt treatments that alter an individual's microbiome and AMP profile to improve patient health; however, this approach has not been adopted for LUTS treatment. Here, we propose the first step in development of such a therapy. If our hypothesis is correct, we could validate estrogens a first line of treatment in hypoestrogenic women. It could also propel the use of an individual's PFM and/or AMP characteristics to develop future personalized therapies to improve treatment response and/or prevent LUTS.

[figure not shown]
**Estrogen improves OAB symptoms:** There is compelling evidence to suggest that vaginal estrogen therapy relieves symptoms of OAB including frequency, urgency and UUI in postmenopausal women [7, 8, 11, 12]. The evidence is sufficient to list the application of vaginal estrogen alone as a treatment option for OAB in the clinical practice guidelines for postmenopausal women with urogynecological complaints [18]. The mechanism of vaginal estrogen's effect on OAB symptoms is poorly understood. Vaginal estrogen has the ability to modify the vaginal microbiome and reduce recurrent urinary tract infections in postmenopausal women [16]. We reason that vaginally applied estrogen would also modify the FUM, which appears to play a role in OAB [1].

**The Bladder is Not Sterile.** Current treatments and preventive strategies are based upon the dogma that the bladder is a sterile environment. Compelling new evidence challenges this long-held belief. Detection of bacterial DNA and isolation of live bacteria from urine taken directly from the bladders of women with and without urinary symptoms has been reported by us [1-3], and by others [4, 5]. However, the role of the female urinary microbiome (FUM) in urinary health and disease is incompletely understood.

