## Methodology

**Power Calculation/Sample Size:** Based on the difference in diversity between UUI and non-UI controls (Fig 1), we were able to do a power analysis and determine that a sample size of 60 will give us sufficient power (0.816), using the Wilcoxon-Mann-Whitney test, to detect the difference between patients whose urinary microbiomes retain high diversity compared to those that change to a low diversity state. Initially, we plan to conduct a pilot study of 20 patients to inform a future, larger funded study.

**Recruitment:** Women will be recruited from the ambulatory urogynecology clinic at Loyola University Medical Center. A total of 60 hypoestrogenic, post-menopausal women will be enrolled as part of a pilot study. The PFM and AMPs will be measured prior to, and following 12 weeks of, vaginal estrogen treatment. Each patient will act as her own control, with her own baseline prior to estrogen treatment. Subjects who meet eligibility criteria and agree to research participation will indicate their consent by signing the research consent form. Subjects will indicate their consent for biorepository storage of leftover urine for potential future IRB-approved studies by signing the biorepository consent form. Consistent with prevalent research regulations and policies, a signed copy of the research and biorepository consent documents will be given to the subject and the investigator will keep the original research consent documents. Participation in the research will not depend upon participation in the biorepository (**Appendix 1**). Please see the ethics and patient consent section for details of the consent process.

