### ***Patient Data Collection:***

**Visit 1 (baseline):** After enrollment and informed consent is obtained, patients will be asked to complete the OAB-q, a validated questionnaire, (**Appendix 3**) to measure OAB-related symptoms and quality of life [17]. Voided urines will be collected in a hat for 16SrRNA, PCR and protein analysis. A perineal swab will then be collected and assessed by 16S rRNA sequencing. Then a 30 mL vaginal lavage will be collected from the anterior wall of the vagina using sterile water for PCR and protein analysis. A vaginal swab will also be collected from the posterior fornix prior to the catheterized urine collection and assessed by 16S rRNA sequencing. Following the collection of the vaginal swab, a post void residual specimen will be collected by transurethral catheter, which is part of our standard practice for new patients. This specimen will be sent for standard clinical microbiology culture, EQUC and 16S rRNA gene evaluation. The specimens destined for the [name] lab will be stored on ice until pick up and transport. The swabs and urine for culture will be stored at room temperature until processed. The urine for sequencing will be refrigerated.

Demographic information and clinical characteristics will be collected, including age, parity, medical illness, previous hysterectomy, previous incontinence surgery, post void residual volume and body mass index (**Appendix 4**).

Physical examination will be completed, including evaluation for pelvic organ prolapse with the POP-q examination, which is part of a standard initial clinical evaluation.

Patients will be counseled on the evidence-based, first-line options for the treatment of OAB, including behavioral modifications, physical therapy, and vaginal estrogen per standard practice in our clinic. All study participants will be provided vaginal estrogen Premarin Cream® 0.625 mg conjugated estrogen/gram and instructed to use 0.5 grams twice weekly with the applicator. This is based on the clinical practice guidelines for vaginal estrogen use in postmenopausal women with urogynecological complaints developed by the Society of Gynecological Surgeons Systematic Review Group [18]. Patients will receive compensation at visit one with a parking voucher.

Patients will be given a medication diary for the use of vaginal estrogen to assess compliance (**Appendix 5**).

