Statistical analyses of the microbiome data (EQUC and 16S rRNA) will be performed using SAS software version 9.4. Descriptive statistics for demographics, clinical characteristics, and microbiome data will be calculated including means with standard deviations, medians with interquartile ranges, or counts and percentages. Medians and interquartile ranges will be presented for OAB-q subscales at each time point as well as a change score, and Wilcoxon signed-rank tests assessed statistical significance of change in OAB-q. Each diversity measure will be modeled as a separate dependent variable in a linear mixed-effects regression, with independent variables including time, OAB-q symptom severity, physical therapy completed, weeks of estrogen compliance, and body mass index, and random intercepts for subjects. Spearman's rho will be calculated for change in Lactobacillus levels associated with change in the OAB-q symptom severity (12-week minus baseline values). For AMP data analyses, Spearman's rho will be used to test associations between change in relative abundance and change in area of bacterial growth inhibition.

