**Expectations:** Since the FUM is more diverse in women with UII than in women without UII, since the bacteria of the FUM are similar to those of the vagina, and since estrogen treatment can reverse the increased diversity of the vaginal microbiome associated with menopause, we predict that estrogen treatment will make the FUM less diverse and improve LUTS. On the basis of our recently published study [1], we expect that hypoestrogenic women with UII, on average, will have 3 different bacterial species as detected by EQUC. We predict that estrogen treatment will reduce this average number towards the average of 1 bacterial species as detected by EQUC in the continent controls from our previous study [1]. In that study, the difference between women with UII and women without UII was highly significant ( $p=0.0001$ ). In the proposed study, we anticipate a smaller difference (since all women will have UII) and will consider significance at  $p<0.05$ . Since 16S sequencing and EQUC provide complementary views of the FUM [1], we anticipate that sequencing will provide similar results; however, sequencing can identify bacteria that are not cultured, even by EQUC, and thus will provide us with a broader view of FUM composition. We predict that AMP levels will correlate with certain microbiota profiles, and anticipate that increased AMPs *via* estrogen supplementation will correlate with improved frequency and severity of OAB symptoms.

**Possible Limitations to the study:** We do not anticipate any problems recruiting and retaining patients, as we have a long track record of similar studies. We anticipate some loss to follow-up (~7%). The timing of the first sample, taken at the first visit, will be necessarily variable but will be about 12 weeks from the commencement of estrogen treatment.

We do not anticipate any problems in the transfer of samples from the Ambulatory Clinic to the Clinical Microbiology Lab or the Genomics Facility, respectively, for culture and sequencing, as we have an established

and successful protocol for such transfer. For similar reasons, we also do not anticipate problems with the culture or sequence analyses.

We know that some urinary bacteria do not grow, even under EQUIC conditions. We also know that some bacteria are not readily sequenced. However, the strengths and weaknesses of EQUIC and sequencing are complementary and thus permit a broad and relatively unbiased view of the bacterial composition of the FUM.

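### The Lactobacillus–symptom change correlation is unadjusted for estrogen use, so it cannot separate a bacterial link from shared dependence on cream use; adding a partial correlation is a cheap improvement

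*Combined protocol and SAP*

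**What the plan says.** The Statistical Analysis Plan paragraph of the Methodology names one change-on-change analysis of microbiome and symptoms: Spearman's "rho will be calculated for change in Lactobacillus levels associated with change in the OAB-q symptom severity", each change taken as the 12-week value minus baseline. It names no covariate, compliance stratum or caveat.

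The preceding sentence treats estrogen use differently. Its covariate list reads "independent variables including time, OAB-q symptom severity, physical therapy completed, weeks of estrogen compliance, and body mass index". That list belongs to mixed models, with random intercepts, whose outcomes are the diversity measures only. Lactobacillus level is not named as an outcome of those models.

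The data for an adjustment should exist. Under Visit 1, "Patients will be given a medication diary for the use of vaginal estrogen to assess compliance". Every woman is "instructed to use 0.5 grams twice weekly with the applicator", and there is no untreated group: "Each patient will act as her own control, with her own baseline prior to estrogen treatment".

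The correlation serves an Aim 2 question: "Do PFM and/or AMP changes correlate with treatment response"?

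**The concern.** By the protocol's own account, estrogen acts on both sides of this correlation. The background section says that estrogen reverses the loss of Lactobacillus after menopause, and under Expectations "we predict that estrogen treatment will make the FUM less diverse and improve LUTS". The Specific Aims also acknowledge that several mechanisms have been proposed for estrogen's effect on urinary symptoms, so symptoms may improve by routes that do not involve bacteria.

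Because the regimen is the same for all and there is no control arm, differences in exposure between women come from how consistently they used the cream. If consistent users gain more Lactobacillus and also improve more, the two changes will correlate even when neither affects the other. The study's idea is that estrogen improves symptoms partly through the microbiome, and a correlation of this kind could be taken as support for that idea when it is not.

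**Working it through.** **The plan's own figure.** The only stated power is 0.816, for a Wilcoxon-Mann-Whitney comparison of women who keep high diversity with those who change to low diversity, at a sample size of 60. Simulated species counts roughly matched to the quoted medians and interquartile ranges give 0.835 or 0.853 for a 30/30 split, and 0.76 to 0.83 for a 20/40 split taken either way round. So 0.816 is plausible near balance, but it cannot be confirmed because the split and distribution are not given. It concerns a different test. No figure is stated for the Spearman analysis.

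**Inputs from the documents.**
- Sample size: 20 (Aim 1) or 60 (Recruitment). The Power Calculation paragraph mentions both.
- Loss to follow-up: about 7%. Pairs: 60 × 0.93 = 55.8, about 56; 20 × 0.93 = 18.6, about 19.
- Significance level: 0.05, stated under Expectations; two-sided is assumed.

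**Assumed, because the documents are silent.** Weeks of use correlate r with Lactobacillus change and -r with severity change (higher severity is worse), and there is no direct link between the two changes.

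**Expected correlation.** With use as the only common cause, the product-moment correlation of the two changes is -r². For normal variables the large-sample Spearman value is -(6/π)·arcsin(r²/2):
- r = 0.2: -(6/π)·arcsin(0.020) = -0.04
- r = 0.3: -(6/π)·arcsin(0.045) = -0.09
- r = 0.5: -(6/π)·arcsin(0.125) = -0.24

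Simulated means at 19 and 56 pairs are about -0.04, -0.08 and -0.23.

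**Rejection rates** (simulation, two-sided 0.05; repeat runs differ by about one percentage point):

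| r (assumed) | Raw rho, 56 pairs | Raw rho, 19 pairs |
|---|---|---|
| 0 | 5% | 5% |
| 0.2 | 6% | 5% |
| 0.3 | 10% | 6% |
| 0.4 | 20% | 9–10% |
| 0.5 | 42–43% | 16–17% |

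If use is bounded, with an assumed 70% of women fully compliant and the rest spread over 0 to 11 weeks, r = 0.5 gives 36% and 16%.

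**Effect of adjustment.** The partial correlation is (ρ_LS − ρ_LU·ρ_SU) / √[(1 − ρ_LU²)(1 − ρ_SU²)], where L is Lactobacillus change, S is severity change and U is recorded use, computed on ranks. When recorded use is exact, the numerator is approximately -r² + r² = 0, and simulated rejection is about 5% over the r values tabulated.

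That result depends on an exact diary. Take r = 0.5 and 56 pairs. With diary reliability λ (assumed), the partial correlation is (-0.25 + 0.25λ)/(1 − 0.25λ):
- λ = 0.7: -0.075/0.825 = -0.09; rejection about 10–11%
- λ = 0.5: -0.125/0.875 = -0.14; rejection about 18–19%

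Differing biological response to the same use is not in the diary at all. If such a response correlates 0.5 with each change and use correlates 0.3 (both assumed), the partial correlation is (-0.34 + 0.09)/(1 − 0.09) = -0.27, and the adjusted test still rejects in about 49% of trials at 56 pairs.

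**The case against.** The strongest reply is that the plan promises only association. Aim 2 asks whether characteristics correlate with symptoms, and the central hypothesis is also worded as association. In the scenario above the two changes really are correlated, so a significant raw rho is a correct answer to that question. This stands. A reader might infer that the planned rho is invalid or yields false positives for Aim 2. The documents do not support that, because the Statistical Analysis Plan attaches no mechanistic conclusion or decision rule to it.

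Second, the rejection rates presume a test. The plan says the Lactobacillus rho will be calculated; it speaks of testing only for the antimicrobial peptide correlation, and the 0.05 level appears in the discussion of species number. This also stands: the rates show how easily a shared cause could look convincing, not the error rate of a declared test.

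Third, nothing in the documents supports r = 0.5. Free cream, a common regimen, a diary and a reminder call before the second visit all suggest limited variation in use. No compliance figure is given, so this argues for caution about size without removing the omission.

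Fourth, adjustment is not a cure, as the diary-error and biological-response calculations show. That changes the fix. It does not make the raw rho sufficient alone.

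Nor should one infer that the plan ignores estrogen use. It names compliance as a covariate in the diversity models, which cover the principal microbiome hypothesis.

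**Conclusion.** The point holds as a cheap improvement. The plan reports only an unadjusted rho for Lactobacillus change against severity change, although a variable it already names is a plausible common cause of both. The raw rho is adequate for association and uninformative about whether the association runs through Lactobacillus.

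The size cannot be fixed from the documents. At an assumed r of 0.2 or below, or with nearly uniform use, the effect is negligible at either sample size. With the 20-woman pilot it stays at about 10% or less up to r = 0.4. It becomes large only with strong dependence on use and the larger sample.

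A reader might also infer that the adjusted rho would establish the mechanism. It would not, because it removes only the part of the shared dependence that the diary captures.

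**What to change.** In the Statistical Analysis Plan, after the sentence on the Lactobacillus correlation, add a partial Spearman correlation adjusted for weeks of estrogen compliance and report it beside the raw rho. State that both are read as association only, because diary error and differing biological response leave residual confounding. Physical therapy may be added to match the mixed model. This is optional: the documents give it no route to Lactobacillus, and the visit procedures do not say how it is recorded.

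Provided use is not itself a response to symptoms, adjusting for it does not remove a genuine Lactobacillus-to-symptom path, since use lies upstream of both. Women may, however, stop because symptoms do not improve, which is a further reason to show both estimates.

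The cost is one sentence and one degree of freedom (two with physical therapy). Women without a returned diary drop out of the adjusted estimate only, so the number contributing to each estimate should be shown. No new visits or samples are needed.

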### **Ethics and Patient Consent**

Patients will be identified when they present to the Loyola Urogynecology outpatient clinic for management of their OAB symptoms. Co-investigators ([name], [name]) will identify and recruit patients for participation. The consent form will be read to the patient; it will describe the nature of the trial and potential associated risks and benefits. Potential participants will be informed that neither participation nor refusal will influence the care received at Loyola University Medical Center. A copy of the consent form will be given to them. Participation is completely voluntary and they may discontinue participation in the study at any time

**Patient Compensation:** Patients will receive a three months' supply of Premarin vaginal cream at no cost. Patients will receive a five dollar parking voucher at both visit one and two for their participation in the study.

